Virtual reality (VR) has expanded in recent years from the personal entertainment industry to the medical field. It has been found in preliminary study to be safe and effective as an adjunct to standard sedative and analgesic protocols in reducing pain and anxiety for patients undergoing upper gastrointestinal endoscopy, dental procedures, dressing changes for burns, and major orthopedic surgical cases (Vazquez 2017, Furman 2009, Morris 2009, Chan 2017). To date, the use of VR during hand and wrist surgery has not been studied to reduce intraoperative anesthetic requirements and improve the postoperative patient experience. A positive result from the proposed study could lead to a change in practice, with the introduction of a non-pharmacologic, patient-led intervention, potentially reducing the burden of unnecessary oversedation while providing a satisfactory perioperative experience.

B3. DESCRIPTION OF RESEARCH PROTOCOL

A. Study Design – Overview, Methods, Procedures

Study Overview

The proposed study is a randomized, controlled trial to evaluate the effectiveness of VR as an adjunct to standard anesthetic practice for hand and wrist surgery. Patients will be randomized to undergo immersion relaxation via the use of VR during their procedure or control. In both groups patients will undergo regional anesthesia preoperatively according to standard practice. Patients will then be assessed postoperatively to assess the intraoperative propofol dose between groups, as well as secondary outcomes including patient satisfaction.

Study Procedures

Patients who meet inclusion criteria with no exclusions will be approached to provide written informed consent in the perioperative period, as detailed below (Section B6). At this time we will provide patients with a study handout to ensure complete understanding of the study (see attached). We will also ask participants to complete a brief survey about how they are feeling at baseline (see attached). This should take about five minutes to complete.

After consent and prior to surgery, patients will be randomized in a 1:1 allocation to either intraoperative VR or usual care control. Given the nature of the intervention, we are unable to blind treatment allocation.

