During their operation, after appropriate positioning has been taken place, the patient will don the VR headset and view the programming of their choice. Study team members will be available intraoperatively to assist with the implementation of the device programming. The relaxation programming will run for the duration of the operative procedure. At any time, the patient or anesthesia provider can decline to continue with the VR programming. At the end of the procedure the VR headset will be removed and standard postoperative care will commence.

Control Group

Subjects in the control group will be asked to refrain from using a VR modality intraoperatively. They will otherwise prepare for surgery and undergo perioperative care according to the current standard of care.

Follow Up

Postoperative care, including management in the PACU, will be conducted to the current standards of care. Data on postoperative outcomes, medications, and pain scores will be collected as indicated below in order to assess secondary outcomes.

After surgery, members of the study team will meet with the patient and ask them to complete a survey about their experience and overall satisfaction with the study. The survey will be built and administered using REDCap. If the patient is unable to complete the survey in-person, a link directly to the REDCap survey will be emailed to them.

Consistent with the current standard of care, patients will return to their surgeon's office for a postoperative visit, which typically occurs one month after surgery. Data from this visit, including surgical outcomes and assessment, will be passively abstracted from their medical record.

Data Collection

In order to assess our primary and secondary outcomes, data will be collected on intraoperative propofol dose, length of

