Data Analysis: Patients will be prospectively randomized using 1:1 block randomization of equal sizes. Analyses will be conducted using SAS version 9.3 (SAS Institute, Cary, North Carolina) or later. Descriptive statistics of the data will be performed. Continuous data will be represented using mean (\pm standard deviation) or median (interquartile range) for variables not normally distributed and compared using parametric or non-parametric t-tests as appropriate. Categorical data will be presented using proportions and compared using a chi-square or Fishers Exact test.

Primary Outcome

The primary outcome of this study is total intraoperative propofol dose, evaluated as a continuous variable. This will be assessed using a t test or Wilcoxon Rank Sum test, depending on the normality of the data. Although randomization should account for potential difference between groups, we will employ univariate and multivariable linear regression modeling to adjust for differences that persist, as necessary. Odds ratios and 95% confidence intervals will be reported. Our primary analysis will be conducted using intention to treat principles.

Secondary Outcomes

A priori secondary outcomes include length of PACU stay, postoperative analgesia dose requirements, postoperative pain scores, and overall patient satisfaction. Differences in time, medication administration and pain scores will be expressed as continuous variables. Patient satisfaction will be assessed from the REDCap survey, and will provide quantifiable estimates of satisfaction in multiple areas including but not limited to pain, anxiety, nausea, and overall experience. Adherence to the randomization assignment will be evaluated, and in the event that any patient receives an intervention different than their randomization assignment, we will also perform a per protocol analysis as an additional secondary outcome. For all secondary analyses, parametric or non-parametric tests will be employed in an analogous fashion to our baseline characteristics between groups.

C. Subject Selection

Inclusion Criteria:

1. Patients undergoing hand or wrist surgery at BIDMC under MAC

Exclusion Criteria:

1. Age < 18
2. Open wounds or active infection of the face or eye area
3. History of motion sickness
4. History of claustrophobia
5. History of seizures or other symptom linked to an epileptic condition
6. Patients who plan to wear hearing aids during the procedure

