It is possible that by virtue of being enrolled in this study participants may receive fewer medications than they would otherwise receive if they did not participate. Risks associated with receiving less propofol include additional movement of the arm, temporary pain or discomfort during surgery, as well as the potential to experience discomfort or anxiety related to being alert in the operating room. If a patient experiences any pain or discomfort, the procedure will be temporarily paused and a local anesthetic injection can be administered. Of note, all patients will receive a nerve block as part of the standard of care for this surgery, regardless of study participation. This nerve block, when properly performed, renders the operative arm insensate and unable to move. Therefore, patients would only experience pain if this block was inadequate, further limiting the risk of experiencing pain. Additionally, participants will be monitored throughout the procedure by the clinical team. Need for additional medications will be consistently assessed throughout surgery, with assessment occurring independently of study participation and in the manner in which the response to surgical stimulation is usually assessed in standard anesthesia practice. .

As with any research study, there is the potential risk of a breach of confidentiality. To minimize the risk of dissemination of health information, all PHI from screening and enrollment will be saved on BIDMC research servers and only coded

information will be included in the REDCap database so as to prevent any unintended dissemination of PHI. No identifiable health information will be exchanged between the VRHealth company and the investigators.

We believe these risks to be outweighed by the benefit of knowledge gained about strategies that could potentially avoid unnecessary oversedation that can sometimes occur with MAC anesthesia.

B6. RECRUITMENT AND CONSENT PROCEDURES

Recruitment

Eligible patients will be identified by operative scheduling lists, surgical clinic visit schedules, and pre-admission testing (PAT) clinic visit scheduling lists. All patients who meet inclusion criteria with no exclusions will be approached in private areas for full written informed consent.

Consent

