Once a patient is determined eligible, s/he will be approached by an IRB approved member of the study team. Informed consent will take place in the preoperative setting, either in a private area of a surgery clinic or PAT clinic. At the time of consent, all study procedures will be explained in detail, including the associated risks and benefits. The subject will have the opportunity to ask any and all questions, and will be reminded that participation is voluntarily and declining to participate will in no way affect their relationship with their health care provider or BIDMC. All subjects will be consented with curtains drawn or the door closed, assuring patient privacy. Written informed consent will then be obtained prior to initiation of any research procedures.

Please see Part A and the attached HIPAA waiver of authorization for additional information.

Subject Protection

It is unlikely that patients will be vulnerable to coercion or undue influence in this study. Although patients of one of the co-investigators ([name]) will be approached for inclusion in this study, consent will be obtained from another member of the study team to ensure patients don't experience any undue influence. Patients will be informed that their decision to participate or not to participate will in no way affect their relationship with their health care provider, the performance or outcome of their upcoming surgery. Patients will also have the ability to discontinue their participation at any time.

B7. STUDY LOCATION

Privacy

All efforts will be taken to ensure patient privacy. Patient interactions including consent will take place in private clinical settings with curtains/doors closed so as to provide privacy and comfort. Throughout the study, only the minimum required information will be collected, assuring patient privacy during the study protocol as with usual patient care. Data collection from chart extraction will occur only on password-protected computers secured by the BIDMC firewall or in REDCap directly. Data collected will be limited to only the minimum necessary to accomplish the stated research purposes.

Physical Setting

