Consent will be obtained from eligible patients in private clinical settings on the BIDMC East Campus, in either [name] hand surgery clinic or PAT clinic, with curtains/doors closed to ensure privacy. Study procedures and follow up will occur in the operating rooms on the East campus and at the surgery clinic, respectively. Data will be abstracted from the patients' chart and will be stored on password-protected computers behind the BIDMC firewall or in REDCap directly. All data collected on paper will be maintained in locked study offices accessible to only the study team. Study investigators have been trained to maintain PHI in a secure and compliant manner.

B8. DATA SECURITY

Data will be stored on password-protected computers behind the BIDMC firewall and entered into a computer database (REDCap). Computers and data collected on paper will be stored in locked study offices. For all analyses subjects will be identified only by their unique coded study ID number assigned for the sole purpose of this project. Limited information will be retained on patients who are prescreened and do not qualify, or who are approached and declined, for the purposes of generating a CONSORT diagram for the trial. At the completion of the study, final, aggregated data may be shared with VRHealth. No identifiable data will be shared.

B9 Multi-Site Studies

N/A – Single Center Study

Is the BIDMC the coordinating site? Yes No

Is the BIDMC PI the lead investigator of the multi-site study? Yes No

B10 Dissemination of Research Results

Please explain whether you will be able to thank subjects and provide research results and, if so, how this will be accomplished. If you do not think this is feasible, appropriate or applicable to this research, please specify why.

Patients will be thanked for their time throughout the study. There is no plan to share the data at the conclusion of the trial. Because study results are likely to be published a year or more after a given subject's participation, it is not feasible to send subjects follow-up with the published results. The study investigators are concerned that mailing the published manuscript and an additional thank-you note years after participation risks violating subject privacy, as mailing addresses are increasingly likely to change with passing time. It is out of the scope of this study to continue tracking mailing addresses after completion of enrollment since this is not a longitudinal study.

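### Equal-size blocks and no stated allocation concealment in an open-label, single-centre trial: if the block is short, staff could deduce some upcoming assignments

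*Combined protocol and SAP*

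**What the plan says.** The method of randomization is given in one sentence of section B3.B (Data Analysis): "Patients will be prospectively randomized using 1:1 block randomization of equal sizes". The Study Procedures part of B3.A adds the ratio and the timing: "After consent and prior to surgery, patients will be randomized in a 1:1 allocation to either intraoperative VR or usual care control". It also states: "Given the nature of the intervention, we are unable to blind treatment allocation".

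Section B9 describes a "Single Center Study". No stratification is mentioned, so I assume one running list.

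On who does what, the Consent part of B6 says: "Once a patient is determined eligible, s/he will be approached by an IRB approved member of the study team". The intervention description in B3.A says: "Study team members will be available intraoperatively to assist with the implementation of the device programming". Recruitment and sight of past assignments therefore sit in the same team.

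Two further statements bear on selection. The Recruitment part of B6 says: "All patients who meet inclusion criteria with no exclusions will be approached in private areas for full written informed consent". Section B8 says: "Limited information will be retained on patients who are prescreened and do not qualify, or who are approached and declined", for use in a CONSORT diagram.

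The document does not give the block length. It does not say who generates or holds the list, whether recruiters are told the scheme, or how the next assignment is kept from them until a patient is committed.

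**The concern.** Because 1:1 already fixes equal arms, the words about equal sizes most naturally describe the blocks. With a constant block size, the end of each block becomes predictable to anyone who knows the size and has seen the earlier assignments. In an open-label trial with one list and one team, the earlier assignments are visible.

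A recruiter who knows the next arm can influence who takes that slot, through how a patient is approached or, if several consented patients are waiting, through the order in which they are randomized. The plan places randomization somewhere between consent and surgery and does not fix the moment. If patients expected to need little sedation tend to go to VR, the propofol comparison is biased in favour of VR.

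Analysis by intention to treat does not help, since the selection happens before randomization. The regression adjustment in B3.B is planned only if needed, with no covariates named.

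**Working it through.** **Inputs from the plan (B3.B).** Means 0.069 (SD 0.03) and 0.042 (SD 0.021), two-sided alpha 0.05, 80% power, 32 patients, raised to 40 (20 per arm).

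**Step 1. Reproduce the plan's own figure.** The difference is 0.069 − 0.042 = 0.027. The root-mean-square SD is √[(0.03² + 0.021²)/2] = 0.0259, so the standardized difference is 1.04. A two-sample t test has 78.7% power with 15 per arm and 81.4% with 16, so 32 reproduces. 32/(1 − 0.20) = 40 reproduces too. The plan gives no figure for predictability.

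**Step 2. Share of assignments that are certain.** Take a known block of size b = 2m. The last l assignments all belong to one arm with probability 2·C(b−l, m)/C(b, m). Summing over l = 1 to m gives the expected number of certain assignments per block. For b = 4 this is 2·3/6 + 2·1/6 = 1.333, and 1.333/4 = 33%. The success rate of the best guess is [m + 2^(2m−1)/C(2m, m) − ½]/b. For b = 4 this is (2 + 8/6 − 0.5)/4 = 71%.

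**Step 3. Bias and type I error under assumed steering.** Assumption: at every certain slot, expected propofol need is lowered by s when VR is next and raised by s when control is next, with s = 0.25 to 0.5 SD. The bias is then 2 × share × s. With 20 per arm the noncentrality is bias/√(2/20) on 38 degrees of freedom.

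| Block size | Certain share | Certain of 40 | Best guess correct | Bias (SD) | Type I error |
|---|---|---|---|---|---|
| 2 | 50% | 20 | 75% | 0.25–0.50 | 12–34% |
| 4 | 33% | 13.3 | 71% | 0.17–0.33 | 8–18% |
| 6 | 25% | 10 | 68% | 0.13–0.25 | 7–12% |
| 8 | 20% | 8 | 67% | 0.10–0.20 | 6–10% |
| 10 | 17% | 6.7 | 65% | 0.08–0.17 | 6–8% |
| 20 | 9% | 3.6 | 62% | 0.05–0.09 | 5–6% |
| 40 | 5% | 1.9 | 59% | 0.02–0.05 | about 5% |

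The row for 6 uses the share per full block, because 40 is not a multiple of 6. For blocks of 4, the bias in the plan's units is 0.167 × 0.0259 = 0.0043 to 0.333 × 0.0259 = 0.0086. Divided by 0.027, that is 16% to 32% of the planned difference. A simulation of the same steering (2,000 runs per case, no true effect) agrees within its error of 1 to 2 points: 8% and 17% for size 4, 11% and 32% for size 2.

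**Step 4. Milder steering, blocks of 4.**
- Staff need the first 8 patients to learn the size: bias × 32/40 = 0.13–0.27 SD, type I error 7.0–13.0%.
- They need the first 12: bias × 28/40 = 0.12–0.23 SD, type I error 6.5–11.1%.
- They steer in one direction only: bias 0.08–0.17 SD, type I error 5.8–8.1%.

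**Step 5. What varying the sizes achieves.** These simulations assume a recruiter who knows the set of sizes.
- Certain assignments fall from 13.3 of 40 (fixed 4) to about 1.6 (mix of 2, 4, 6) or 1.0 (mix of 4, 6, 8). A mix of 4 and 6 leaves about 6% certain.
- With 0.5 SD steering at certain slots only, bias falls to 0.02–0.04 SD and type I error to about 5%.
- The best-guess rate hardly moves: 71% for fixed 4, 70% for 2/4/6, 69% for 4/6 and 68% for 4/6/8.
- If recruiters acted on every best guess at 0.5 SD, type I error would be about 22% with fixed 4, 22% with 2/4/6 and 17% with 4/6/8.

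**The case against.** The strongest reply is that the risk is conditional. Deducing an assignment needs a short block and staff who know or infer its length, and the plan states neither. A reader might infer that staff will know many upcoming assignments for certain. The text does not support that: at sizes 20 or 40 the certain share is 9% or 5% and type I error stays near 5%. The wording could also mean equal groups, which would match the planned 20 per arm. This reply stands. It is why the point is put conditionally and the whole range of sizes is shown.

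The plan also has real safeguards. Randomization follows consent, every eligible patient is to be approached, the eligibility criteria are mostly factual, and the limited records of patients who do not qualify or who decline would let selective approach be audited. These steps leave little room for openly passing over patients. They do not govern how persuasively a patient is approached or the order in which consented patients are randomized, and an audit comes after the event.

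Finally, equal block size is only part of the problem. A reader might conclude that varying the sizes alone would settle it. Step 5 shows otherwise: certainty goes, but guessing stays. A fixed block of undisclosed length with central release would answer much of the concern. So concealment deserves equal weight. Varying the sizes is still worth adding, since a fixed length can be learned from assignments the team sees.

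**Conclusion.** The point holds as a conditional weakness that should be corrected. On its natural reading, the plan specifies one block size in an open-label, single-centre trial whose team recruits and sees assignments, and it describes no concealment. If the block is short and its length becomes known, between a quarter (size 6) and a half (size 2) of assignments could be deduced. For longer blocks the share falls to 5%.

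The type I error figures rest on three assumptions that are not in the plan: the block length, steering of 0.25 to 0.5 SD in both directions, and its use at every certain slot from the first patient. For steering confined to certain slots they mark the upper end. They show what the design leaves open; nothing in the document shows that steering would occur.

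The treating provider, who is not blinded, sets the propofol dose. That is a separate source of bias, which concealment would not cure.

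**What to change.** Replace the randomization sentence in B3.B with:

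> 1:1 permuted-block randomization with randomly varying block sizes that are withheld from recruiting staff; the list is generated by someone with no patient contact, and each assignment is released in REDCap only after consent and eligibility are recorded.

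The withheld sizes and the concealed release are essential, because varying the sizes removes most of the certainty but little of the guessing.

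The cost is one sentence, a new list and setting up the release step. REDCap is already used for surveys and data, although the plan does not say it is used for randomization. The sample size stays at 32, or 40 with dropout. The downside is a possible arm imbalance of a few patients if the last block is incomplete: an unfinished block of 6, for example, can leave the arms at most 3 apart.

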In both groups patients will undergo regional anesthesia preoperatively according to standard practice. Patients in the VR group will undergo immersion relaxation via the use of a VR headset and software packages for their intraoperative course as an adjunct to standard anesthesia practice. Control patients will undergo usual anesthesia care as determined by their anesthesia provider, without the addition of the VR device. All intraoperative anesthetic management and medication administration will be at the discretion of the treating provider. Patients will be monitored (vital signs, capnography) according to ASA standards for a MAC anesthetic. This data will be passively abstracted from the medical record in order to assess study outcomes.

It is possible that by virtue of being enrolled in this study participants may receive fewer medications than they would otherwise receive if they did not participate. For example, an anesthesia provider may not administer the initial bolus of pre-procedure propofol for a patient in the VR group, but instead continue to monitor them and only administer it if/when needed clinically. This potential for divergence from the standard process is well within clinically acceptable standards of care, but has been described as a potential risk associated with participation. In both groups patients will be monitored by their anesthesiologist, assessed and treated as necessary. The assessment is conducted by the clinical anesthesiologist independent of their participation in the study or study group assignment.

Intervention: Virtual Reality Immersive Relaxation

The intervention to be studied in the proposed trial is a relaxing, immersive virtual reality environment. Immersion takes place by wearing a VR headset connected to a software platform on an iPad. There are various environments that have been created with VR software, all designed to promote relaxation and calmness. Examples include sitting in a canoe on a river, a peaceful meadow or forest, or sitting on a mountaintop. To ensure comfort with the VR setting, patients in the intervention group will be allowed to select from one or several of the prespecified intraoperative relaxation packages, consistent of programs such as those mentioned above.

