PACU stay, as well as postoperative analgesia administration and pain scores. In addition, study team members will review the patients' medical records to collect demographic data and surgical characteristics including intraoperative vital signs, medication administration, and postoperative outcome data. Postoperative pain scores (i.e. 'Rate your pain on a scale from 0 to 10') are documented routinely as part of standard postoperative clinical care, and will be recorded at admission to the PACU and at PACU discharge. Additional baseline characteristics including but not limited to age, race, gender, BMI and comorbidities will be abstracted from the medical record. REDCap will be utilized for survey administration, data collection and storage.

Safety Monitoring and Reporting

This patient population is undergoing surgery and it is expected that they may have a number of unrelated adverse health events during their hospital course. Therefore, we will limit the scope of AE monitoring and reporting to the following:

- All Serious Adverse Events believed to be related to the study procedures
- All non-serious Adverse Events believed to be related to the study procedures

Adverse events will be monitored until the time of PACU discharge.

B. Statistical Considerations

Sample Size Justification: Using a two sided α of 0.05, 80% power, and mean propofol doses of 0.069 (standard deviation 0.03) and 0.042 (SD 0.021), we anticipate needing to enroll a total of 32 patients to be able to detect a 50% reduction in the mean total intraoperative propofol dose. We believe this to be a reasonable effect size given preliminary data from a related study in which investigators were able to demonstrate a >50% reduction in dose for major joint surgery (Chan 2017). In order to compensate for anticipated drop out, we will plan to enroll an additional 8 patients to bring the total planned enrollment to 40 patients, with 20 in each of the two groups.

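### Primary outcome: regression only for unspecified imbalance, with no rule on which result governs, and an odds ratio that a linear model of dose cannot give

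*Combined protocol and SAP*

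**What the plan says.** Section B3.B, Primary Outcome, makes total intraoperative propofol dose a continuous primary outcome. On the test it says: "This will be assessed using a t test or Wilcoxon Rank Sum test, depending on the normality of the data". On adjustment: "we will employ univariate and multivariable linear regression modeling to adjust for differences that persist, as necessary". On the effect measure: "Odds ratios and 95% confidence intervals will be reported". The only further rule for the primary analysis is intention to treat.

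No covariate is named for the regression. Data Collection (B3.A) lists variables to abstract, not variables to model: "Additional baseline characteristics including but not limited to age, race, gender, BMI and comorbidities will be abstracted from the medical record". The sample size rests on an unadjusted comparison, "mean propofol doses of 0.069 (standard deviation 0.03) and 0.042 (SD 0.021"), with 32 patients needed and 40 enrolled, "with 20 in each of the two groups".

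**The concern.** Three things are left open or do not fit together.

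- **Effect measure.** A linear regression of dose on arm estimates a difference in mean dose. No odds arise from it, so the promised measure cannot be produced for this outcome.
- **Which result governs.** If the regression is run and falls on the other side of 0.05 from the t or Wilcoxon test, the plan does not say which result is the trial's answer. Treatment is unblinded, so the written plan is the main safeguard.
- **When to adjust.** Adjustment helps mainly by removing outcome variation that baseline covariates explain, and it does so whether or not the arms happen to be imbalanced. Waiting for a visible imbalance gives up most of that benefit while still adding a second result.

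**Working it through.** **Inputs.** From Sample Size Justification (B3.B): means 0.069 and 0.042, SDs 0.03 and 0.021, two-sided 0.05, 32 evaluable (16 per arm), 40 enrolled (20 per arm). No units are given; I read the figures as total doses. The text speaks of powering to "detect a 50% reduction in the mean total intraoperative propofol dose", whereas 0.027/0.069 = 39.1%. I use the means and SDs because they reproduce the stated 32; the wording and the figures need reconciling separately.

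**The plan's own figure.** Difference 0.069 - 0.042 = 0.027. Root-mean-square SD = sqrt((0.03² + 0.021²)/2) = 0.0259. Standardised effect d = 0.027/0.0259 = 1.043. Noncentral t power, with noncentrality d × sqrt(n/2), is 78.7% at 15 per arm, 81.4% at 16 and 89.5% at 20. So 16 per arm, 32 in all, is reproduced.

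**Always-fitted adjusted model.** With k covariates, residual variance is multiplied by (1 - R²), chance imbalance multiplies the variance by about 1 + k/(2n - 3 - k), and df = 2n - 2 - k. For n = 16 and k = 2 the imbalance factor is 1 + 2/27 = 1.074. R² is an assumption: the documents give no association between any baseline variable and dose. Power for k = 2:

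| R² | 0 | 0.05 | 0.1 | 0.2 | 0.4 |
|---|---|---|---|---|---|
| 16 per arm (unadjusted 81.4%) | 78.5% | 80.5% | 82.5% | 86.7% | 94.3% |
| 20 per arm (unadjusted 89.5%) | 87.7% | 89.3% | 90.8% | 93.6% | 98.0% |

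Break-even R² is 0.073 at 16 per arm and 0.057 at 20; with one covariate it is 0.036 and 0.029.

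**Imbalance-triggered adjustment.** The plan states neither a trigger nor a normality cut-off, so both are assumed. The unadjusted rule uses Wilcoxon if a Shapiro test gives p<0.05 in either arm, otherwise t. A covariate enters the regression if its baseline comparison gives p<0.05 (at least one enters in about 10% of trials) or p<0.20 (about 36%). Simulated power, normal doses, two covariates, 16 per arm, 6,000 trials per cell (standard error about 0.5 point):

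| R² | 0 | 0.1 | 0.2 | 0.4 |
|---|---|---|---|---|
| Unadjusted rule | 81% | 81% | 81% | 81% |
| p<0.05 trigger | 80% | 81% | 82% | 82% |
| p<0.20 trigger | 79% | 81% | 82% | 85% |
| Always adjusted | 78% | 82% | 87% | 94% |

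**How often the verdicts differ.** Share of trials, at the design effect, in which the unadjusted rule and the regression fall on opposite sides of 0.05 (triggered rows 5,000 trials per cell, always-fitted rows 6,000):

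| R² | 0.1 | 0.2 | 0.4 |
|---|---|---|---|
| 16 per arm, p<0.05 trigger | 1.3% | 1.8% | 2.7% |
| 16 per arm, p<0.20 trigger | 4.0% | 5.6% | 7.4% |
| 16 per arm, always fitted | 8.8% | 11.3% | 15.6% |
| 20 per arm, p<0.05 trigger | 1.0% | 1.4% | 2.1% |
| 20 per arm, p<0.20 trigger | 3.1% | 3.5% | 5.6% |
| 20 per arm, always fitted | 5.7% | 6.7% | 9.0% |

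A repeat simulation of the triggered plan gives about 2-2.5% and 5-7.5% at 16 per arm, and about 1-2% and 3-6% at 20, which agrees apart from small simulation differences.

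**Where adjustment loses.** For lognormal doses with the same means and SDs, 16 per arm and R² 0 / 0.1 / 0.2 / 0.4, the unadjusted rule has 89 / 88 / 88 / 89% power and the raw-scale adjusted model 82 / 84 / 88 / 94%. A repeat at R² = 0 gives 87.9 against 82.2%, a loss of 5.7 points. With 20% zero doses in the VR arm, the figures are 70 against 65% at R² = 0 and 72 against 71% at 0.2.

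**Type I error.** Over the null runs, the unadjusted rule gives 4.7-6.3%, the p<0.05 trigger 3.8-5.8% and the always-adjusted model 4.4-5.5%.

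**The case against.** The strongest reply is that nothing invalid is planned. The t or Wilcoxon test comes first, matches the sample-size calculation, and holds its error rate near 5%. The odds-ratio sentence may be carried-over wording that no analyst would follow literally. One sentence naming the unadjusted test as primary would settle which result governs. All of this stands, and it is why replacing the primary test is an option and not a required correction. It does not supply the covariates, the trigger or a usable effect measure.

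Three stronger readings are tempting, and the documents do not support them.

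- *The two analyses will conflict in 9-16% of trials (6-9% at 20 per arm).* Those rates need an adjusted model that is always fitted. The plan fits one only when differences remain; otherwise there is no second result to conflict. For the triggered plan they are roughly two to six times too high.
- *Type I error is inflated.* It is if the more favourable result is picked: taking the better of the t test and the adjusted model gives 6.6 / 7.3 / 7.9% at 20 per arm for R² 0.1 / 0.2 / 0.4. The plan does not prevent this, but nothing in it says that it will be done.
- *Adjustment will raise power.* That depends on an R² the documents do not give. Study Procedures (B3.A) offers a reason to expect a low one: "All intraoperative anesthetic management and medication administration will be at the discretion of the treating provider". The same section says the initial bolus may be withheld in the VR group, so zero or skewed doses are plausible, and there the raw-scale model can lose power.

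It is also fair to say that 16 per arm assumes all eight allowed dropouts occur. The outcome is intraoperative and taken from the record, so 20 per arm, with 89.5% unadjusted power, may be nearer the mark.

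**Conclusion.** The point holds in a limited form. The odds ratio is wrong as written, and this needs no assumption. The regression is under-specified: covariates, trigger and precedence are all missing. Adjusting only on observed imbalance gains about 1 power point (p<0.05) or at most about 4 (p<0.20) for R² up to 0.4 at 16 per arm, against about 13 points (94.3 - 81.4) for a model always fitted at R² = 0.4. The chance that the missing precedence rule decides the trial's verdict is modest: about 2-2.5% or 5-7.5% at 16 per arm and about 1-2% or 3-6% at 20, depending on the trigger.

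These figures rest on the stated means and SDs being total doses, normal doses, two covariates, the design effect being true, assumed triggers, and R² between 0.1 and 0.4. The unadjusted test remains a valid primary analysis.

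**What to change.** Before any dose data are seen, amend Primary Outcome (B3.B) in three places.

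1. Replace the odds ratio with the difference in mean total propofol dose and its 95% CI.
2. Say which analysis is primary, either the t/Wilcoxon test (with its normality criterion) or a fixed adjusted model, and that its result governs whatever the other shows.
3. Replace the imbalance-driven regression with one linear model of dose on arm plus one or two baseline covariates named now: BMI, already collected, and scheduled operative duration or procedure class if it can be abstracted. Fit it whatever imbalance is seen. Never include actual duration: it arises after randomisation and can depend on arm, since B5 allows the procedure to be paused for discomfort.

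**Cost.** A few sentences, at most one extra abstraction field, and one or two degrees of freedom. If the unadjusted test stays primary, its power is unchanged. If the adjusted model is made primary and the covariates do not predict dose, power falls by about 2-3 points with normal doses (81.4 to 78.5% at 16 per arm, 89.5 to 87.7% at 20) and by about 6 with skewed doses at 16 per arm. Where marked skew or zero doses are expected, keep the unadjusted test primary and the fixed model supportive. If the Wilcoxon test is then the one used, the report should say that its p-value and the mean difference come from different analyses.
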